2.4.4 Sensitivity analyses

Not Applicable

2.4.5 Supplementary analyses

Not Applicable

2.5 Analysis supporting secondary objectives

The secondary objectives of this study are to (1) evaluate the incidence and characteristics of diarrheal illness (PD analysis set), (2) to evaluate the time to onset and resolution of *Cryptosporidium* infection (PD analysis set), and (3) to assess the safety and tolerability of ABO809 (Safety analysis set).

2.5.1 Secondary endpoint(s)

The secondary endpoints include the presence of clinical symptoms (diarrheal and associated symptoms) by Day 10 and Day 28, *Cryptosporidium* infection up to Day 28, time to infection and symptom onset, time to resolution of infection (number of days to resolution of Cryptosporidium infection) and diarrheal illness, and characteristics of clinical signs and symptoms associated with diarrheal illness, as well as safety and tolerability assessments up to Day 28 and the 12 month post-study follow-up.

Presence of clinical diarrheal illness will be determined by analysis of diarrhea data: number of days to diarrhea onset (first day with Grade 3 or higher stool), number of days of diarrhea (stool grade 3-5), number of days to resolution of diarrhea (stool grade 1-2), number of diarrheal episodes, total stool output (weight in grams) and the worst (highest number) stool grade each day will be recorded.

Data on other gastrointestinal symptoms associated with *Cryptosporidium* infection will be recorded as follows: presence (yes/no), onset, severity (mild, moderate, severe), therapeutic intervention (yes/no; if yes, what) and progression (ongoing, resolved). These gastrointestinal symptoms include:

- abdominal pain or discomfort
- abdominal tenderness
- abdominal rebound
- abdominal distension
- fecal urgency
- nausea
- vomiting
- flatulence
- tenesmus
- poor appetite
- presence of blood
- fever
- dehydration
- electrolye imbalance

The number of days to gastrointestinal symptoms onset will be defined as the date of the first symptom minus the dosing date.

2.5.2 Statistical hypothesis, model, and method of analysis

The number and percentage of participants with clinical symptoms (diarrheal and associated symptoms) (by Day 10 (inclusive) and Day 28) and with *Cryptosporidium* infection up to Day 28 will be tabulated by treatment group. The 2-sided 80% exact confidence interval of the clinical symptom rate will be reported by treatment group.

Frequency and percentage will be presented for categorical data such as grading of stool, evidence of occult blood in stool and number of diarrhea episodes. Mean, standard deviation, median, minimum, and maximum will be presented for continuous data such as stool weight. Overlaying individual stool weight-time profiles will be generated.

Time to onset and time to resolution of infection and diarrheal illness will be summarized using Kaplan-Meier graphs with separate lines by treatment group. Median time to event for each treatment group will be estimated along with 90% confidence intervals.

Duration of infection and diarrheal illness will be summarized by treatment group.

2.5.3 Handling of intercurrent events

Stool data with grade <3 will be set to missing after the participant took the rescue medication. For "Number of days of ...", "Duration of ...", "Stool output (weight)" variables, data will be right censored if the participant took the rescue medication. Proc Lifetest and Proc Lifereg will be used to calculate the median and mean (SE), respectively. If there are convergence issues with Proc Lifereg for some visits such as those starting on Day 21 when most measurements are censored then Proc Means will be used instead.

For all Kaplan-Meier graphs, participants will be censored under the following circumstances:

- If the study ended before the subject experienced the event.
- If the subject discontinued the study before experiencing the event.
- If the subject died before experiencing the event.
- If the subject took the rescue medication before experiencing the event.

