Outpatient follow-up period: After the domicile period, participants will be followed on an outpatient basis ending on Day 56 following the ABO809 administration. Infection is expected to be self-limiting in healthy adults and resolve by Day 21. Published literature on the intensity of infection and oocyst excretion patterns of *C. parvum* in healthy volunteers suggests that oocyst excretion is limited to the first 14 days in up to 86% participants with diarrhea, and excretion prolonged beyond 28 days is observed in only 5% of participants (Chappell et al 1996). Participants will return for follow-up visits on Day 14, 17, 21, 24 and 28 for physical examination and/or to provide collected stool samples (for measurement of oocyst shedding) (see Table 8-1). Safety Follow-Up Calls will be conducted with participants up to Day 56 to collect adverse events that are considered related to administration with ABO809 (see Section 10.1.1.1). Any participants who experience diarrheal symptoms between Day 28 and Day 56 may provide a stool sample for analysis and may return to the study site for an unscheduled visit to consult with the Investigator.

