2.3.4 Prior, concomitant and post therapies

Prior and concomitant medications will be coded according to the latest version of World Health Organization (WHO) Drug Reference List dictionary which employs the Anatomical Therapeutic Chemical (ATC). The number and percentage of participants taking prior and concomitant medications may be tabulated for each treatment by ATC class and PT. Concomitant rescue and other medications, procedures, and significant non-drug therapies may also be summarized by ABO809 treatment group and cohort number.

Prior medications are defined as drugs taken and stopped prior to first dose of study medication. Any medication given at least once between the day of first dose of study medication and the last day of study visit will be a concomitant medication, including those which were started before dosing and continued into the treatment period.

Rescue medication nitazoxanide

To minimize the risk of severe clinical illness, long-term asymptomatic shedding and recurrence of *Cryptosporidium* infection, nitazoxanide will be administered on Day 21 to all participants who receive ABO809 and develop a *Cryptosporidium* infection, whether or not clinical symptoms are observed.

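### SAP 2.5.3 right-censors measured stool weight after rescue as if it were a survival time, which biases the Lifereg mean upward by an amount the documents do not fix

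*SAP*

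**What the plan says.** Four statements on stool weight in the SAP have to be read together.

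- **Ordinary summary.** SAP 2.5.2: "Mean, standard deviation, median, minimum, and maximum will be presented for continuous data such as stool weight". Protocol 12.5.1 promises the same statistics, and SAP section 4 declares no change from the protocol's analyses.
- **Censoring.** SAP 2.5.3 names three kinds of variable (day counts, durations, stool output by weight) and says of them: "variables, data will be right censored if the participant took the rescue medication". It adds: "Proc Lifetest and Proc Lifereg will be used to calculate the median and mean (SE), respectively". It gives neither the value at which a weight is censored nor the Lifereg distribution.
- **Fallback.** If Lifereg has convergence problems "for some visits such as those starting on Day 21 when most measurements are censored then Proc Means will be used instead". The reference to visits shows that the estimation is done visit by visit.
- **Deletion.** The same paragraph opens: "Stool data with grade <3 will be set to missing after the participant took the rescue medication". It does not say whether weight counts as stool data.

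On who is rescued, SAP 2.3.4 states that "nitazoxanide will be administered on Day 21 to all participants who receive ABO809 and develop a" Cryptosporidium infection, with or without symptoms. Participants whose diarrhea persists to Day 10, or is severe, may be treated earlier.

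**The concern.** Right-censoring suits a quantity that was still accumulating when observation was cut off, such as the duration of an illness interrupted by treatment. A stool weight is complete once the stool is on the scale. Censoring a 180 g weight tells the model only that the value lies above 180 g, so every censored weight pulls the fitted mean up.

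The implied premise, that output would have been larger without nitazoxanide, has little support for participants treated on Day 21 by schedule. Protocol 4.1 expects infection in healthy adults to resolve by Day 21 and cites literature in which "oocyst excretion is limited to the first 14 days in up to 86% participants with diarrhea". No estimand supplies the premise either: SAP 1.2.2 marks secondary estimands as not applicable.

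Stool weight is a listed secondary endpoint, and the study is meant to characterise a challenge model for later efficacy trials. An inflated post-treatment profile would misinform their design, and SAP 2.5.5 plans no sensitivity analysis that would expose it.

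**Working it through.** **No figure to reproduce.** The documents state no stool weight, spread, censored share or bias, so the check is conditional.

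**Inputs from the documents.** Protocol 12.8.1 assumes 90% infected and evaluates a group of 30. Protocol 6.5.1 uses 80%-90% infected as its criterion for staying at a dose. Since all infected participants are rescued by about Day 21, the censored share on Days 24 and 28 is roughly the infected share: 0.90 × 30 = 27, or 0.80 × 30 = 24. Two lower shares were added: 20 of 30 (67%), and 6 of 30 (20%) to illustrate visits with only early rescue.

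**Assumptions not in the documents.** Lognormal weights, mean 150 g (arbitrary; only ratios are used), CV 0.3, 0.5 or 0.8; the same distribution in rescued and non-rescued participants; weights of grade 1-2 stools kept; censoring at the observed weight.

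**Formula.** An uncensored weight y contributes its density f(y) to the likelihood; a censored one contributes only P(Y > y). For the exponential model the fitted mean is the sum of all weights divided by the number uncensored, so its ratio to the ordinary mean is 1/(1 − c), with c the censored share:

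- 27 of 30: 30/3 = 10
- 24 of 30: 30/6 = 5
- 20 of 30: 30/10 = 3
- 6 of 30: 30/24 = 1.25

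**Simulation for more flexible models** (n=30, maximum likelihood, median ratio over 150 runs):

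| CV | Censored | Normal | Weibull | Lognormal |
|---|---|---|---|---|
| 0.3 | 24 of 30 | 1.55 | 1.57 | 1.71 |
| 0.3 | 27 of 30 | 1.81 | 1.86 | 2.30 |
| 0.5 | 24 of 30 | 1.90 | 2.05 | 2.52 |
| 0.5 | 27 of 30 | 2.41 | 2.78 | 4.57 |
| 0.8 | 24 of 30 | 2.38 | 2.76 | 4.37 |
| 0.8 | 27 of 30 | 3.08 | 4.23 | 10.11 |

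The lognormal entries at 27 of 30 rest on three uncensored values and are unstable: separate runs of the CV 0.8 cell gave between about 7.5 and 10. At 20 of 30 the same three models gave about 1.3 to 2.5, and at 6 of 30 an excess of 6-18%. An ordinary mean of the same weights has ratio 1.00.

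**If the deletion rule covers weight.** A rescued participant with only grade 1-2 stools then contributes nothing. Rescued participants are represented only by grade 3-5 stools, which are still right-censored. To the extent that diarrheal output is heavier, the mean is biased upward by selection. The documents allow no figure for this.

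**When the fallback fires.** With 24 or 27 of 30 censored, every fit converged. With 9 of 10 censored, about 9%-15% of non-exponential fits failed. With all values censored no finite estimate exists; at 90% infection and independent outcomes, that happens in 0.9^10 = 35% of cohorts of 10. SAP 2.1.1 reports by pooled treatment group and also by cohort, so the inflated estimator could be used for a pooled group while Proc Means is used for one of its cohorts.

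**The case against.** A reader might infer that the plan will more than double mean stool output on Days 24 and 28 in recovered participants. The documents do not support that, for three reasons.

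- **The size is not derivable.** It depends on an unnamed distribution, an unknown spread and an unstated censoring value. Several plausible cells above lie below 2.
- **The deletion rule may remove those participants.** If it reaches weight, recovered participants leave the mean altogether and no rise could appear in them.
- **The fallback names these visits.** The text expects trouble "such as those starting on Day 21 when most measurements are censored then Proc Means will be used instead", and where it applies the censoring inflation disappears.

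All three stand as limits on the size. None repairs the rule. Deletion replaces one upward bias with another, and the fallback acts on numerical failure, which was absent in groups of 30.

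Two further points have some force. For a participant rescued because of persistent or severe diarrhea, treating post-rescue weight as a lower bound on untreated output is coherent, though strong; but the SAP states no such target and applies the rule equally to scheduled Day 21 treatment. And the literature in Protocol 4.1 concerns oocyst shedding, so it is only indirect evidence that rescue leaves stool weight unchanged; the simulation takes that as an assumption.

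**Conclusion.** The rule is wrong for stool weight and should be changed. The upward direction follows from the likelihood. The size does not come from the documents: about 1.5-fold to several-fold at 80-90% censored, 1.3- to 2.5-fold at 67% and 6-18% at 20%, for normal, Weibull or lognormal fits to assumed lognormal weights with CV 0.3 to 0.8, n=30 and no rescue effect. An exponential fit would be worse. These figures also require that grade 1-2 weights are kept, that Lifereg converges, and that censoring is at the observed weight, which is the natural reading but is not written down.

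Even where the inflation does not arise, the unclear reach of the deletion rule and the convergence-driven change of estimator leave late-visit means not reliably comparable across visits and dose groups.

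The point does not extend to the day-count and duration variables. Nor does it touch the primary analysis or dose adjustment, which under Protocol 6.5.1 relies on infection and clinical symptoms to Day 10 together with safety data. SAP 2.5.2 also plans individual stool weight-time profiles, which would help a careful reader. This is a correction to a descriptive secondary endpoint.

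**What to change.** In SAP 2.5.3:

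1. Delete stool output (weight) from the right-censoring rule, and with it the use of Lifetest, Lifereg and the Proc Means fallback for weight.
2. Summarise observed weight per collection day with the statistics already listed in SAP 2.5.2. Show data before and after nitazoxanide start separately, or restrict the main summary to pre-rescue days.
3. State that the rule setting post-rescue stools below grade 3 to missing does not apply to weight.

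The cost is a change of SAP wording and simpler programming; no new data are needed. The downside is that post-rescue weights describe treated participants and must be labelled as such.

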2.1.1.1 Definition of clinical and parasitological response

Diarrhea: A participant will be considered as having diarrhea if they have at least one stool sample grading 3-5 on the Stool Grading System (Table 5-5). Grade 1-2 stools are considered normal and are formed or soft stool which do not easily take the shape of the container. Grade 3-5 stools are considered diarrheal and are thick liquid, opaque watery, rice water or clear watery stool which do take the shape of the container.

Number of days to diarrhea onset: is defined as the first diarrhea stool date minus the dosing date.

Number of days of diarrhea: is defined as all days with at least one stool sample grading 3-5.

Number of days to resolution of diarrhea: is defined as the last diarrhea stool date minus the dosing date +3

Duration of diarrhea (hours): is defined as the last diarrhea stool date/time minus the first diarrhea stool date/time.

Clinical diarrheal illness: A participant will be considered as having clinical diarrheal illness if diarrhea is observed with at least two diarrheal bowel events within 24 hours on at least two days during the observation period beginning after ABO809 administration (Day 1) and ending on Day 28.

Resolution of clinical diarrhea illness: A participant will be considered recovered from diarrheal illness when no diarrhea occurred on ≥ 2 consecutive days following the last diarrhea in participants with clinical diarrhea illness.

Number of days to clinical diarrhea onset: is defined as the first day of clinical diarrhea illness date minus the dosing date.

Number of days of clinical diarrhea illness: is defined as all days of diarrhea in participants with clinical diarrhea illness. It will be set to 0 for participants with no clinical diarrhea illness.

Confidential

Number of days to resolution of clinical diarrhea illness: is defined as 48 hours after the last day of clinical diarrhea illness, i.e., last diarrhea date minus the dosing date +3 in participants with clinical diarrhea illness.

Duration of clinical diarrheal illness (hours): is defined as the last diarrhea date/time minus the first diarrhea date/time in participants with clinical diarrhea illness.

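### The SAP censors durations because rescue was taken, not because the episode was still running, and its Proc Means fallback then ignores censoring

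*SAP*

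**What the plan says.** SAP 2.5.3 covers three kinds of variable: number of days, duration, and stool output by weight. For these, "data will be right censored if the participant took the rescue medication". No censoring time is given. On method, "Proc Lifetest and Proc Lifereg will be used to calculate the median and mean (SE), respectively". If Lifereg has convergence problems, the SAP provides that "for some visits such as those starting on Day 21 when most measurements are censored then Proc Means will be used instead".

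The list for Kaplan-Meier graphs in the same section is worded differently. There, rescue censors a participant only under this condition: "If the subject took the rescue medication before experiencing the event".

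On who receives rescue, SAP 2.3.4 states that "nitazoxanide will be administered on Day 21 to all participants who receive ABO809" and develop an infection, with or without symptoms. The same section allows earlier starts: once the Day 17 result is known, on Day 10 if diarrhea has persisted, or at any time for severe illness. Protocol 6.2.3 agrees. Protocol 3.3 and SAP 1.1 use permissive wording instead.

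SAP 2.1.1.1 defines each duration as one value per participant, the last event minus the first. SAP 2.5.2 commits to summarising duration of infection and of diarrheal illness by treatment group, and SAP 2.5.5 plans no sensitivity analysis.

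**The concern.** An episode that began and ended before rescue has a fully observed length, and later nitazoxanide cannot change it. The duration rule nevertheless censors it, because its trigger is that rescue was taken at all. In this trial rescue is a scheduled step for everyone infected, so the trigger applies to almost the whole group whose durations are of interest.

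The fallback is a separate problem. Proc Means carries no censoring indicator, yet the SAP turns to it "when most measurements are censored then Proc Means will be used instead".

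At stake are the descriptive summaries of how long infection and illness last. Protocol 1.1 and 1.2 say that the model is meant to support later drug and vaccine trials, and duration is an obvious planning input for those.

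**Working it through.** The documents give no figure for the duration analysis, so there is none to reproduce. The inputs n = 30 and 90% infection come from Protocol 12.8.1, whose own statement checks out. With 26 or more of 30 infected (chance 0.825 at a true 90%), the one-sided 80% exact lower limit is 0.786, against the stated 78%.

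**1. Censored durations under the literal rule.** Infected: 30 × 0.90 = 27. All are scheduled for rescue, so 27 of 27 infection durations are censored and none is observed. At n = 20 and n = 60 the counts are 18 of 18 and 54 of 54.

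**2. Consequence for the median.** With no events the Kaplan-Meier curve stays at 1 and has no median. Suppose one infected participant takes no rescue and supplies the only event. The curve then drops to 1 − 1/r, where r is the number at risk. It reaches 0.5 only if r ≤ 2, a chance of about 2/27 = 7%. Simulation gave about 7%, 14% and 21% for one, two and three such participants.

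**3. Consequence for the parametric mean.** Taking an exponential model as an example (the SAP names no distribution), the log-likelihood with no events is −T/θ, where T is total follow-up and θ the scale. For one simulated set of 27 with T of about 205 days, it is −20.5, −2.05 and −0.21 at θ = 10, 100 and 1000. It rises toward 0 without a maximum, so there is no finite estimate. The literal rule would itself trigger the fallback.

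**4. Censored durations if event order counts.** Protocol 4.1 expects infection to resolve by Day 21. It reports that "oocyst excretion is limited to the first 14 days in up to 86% participants with diarrhea" and that 5% shed beyond Day 28. Taking 86% at face value, the share still shedding at a Day 21 rescue lies between 5% and 14%:
- 27 × 0.05 = 1.35
- 27 × 0.14 = 3.78

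So about 1 to 4 of 27 are censored. A distribution was then assumed for the end of shedding: 3 days plus a lognormal passing through 86% at Day 14 and 95% at Day 28. About 25 of 27 were observed on average, and the median was estimable in all 3,000 simulated trials. The simulations measured time from dosing, because the documents give no distribution from onset. They placed all rescue on Day 21, so earlier rescue would add to the censored count.

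For diarrhea, Protocol 4.1 gives median onset at 3 to 11 days and median duration of 2.3 to 7 days. Simple sums (3 + 2.3 = 5.3; 11 + 7 = 18) suggest that typical episodes also end before Day 21.

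**5. Size of the fallback bias.** Under the same assumed distribution, the mean time to end of shedding is 9.57 days. Cutting values at Day 21 and averaging them as complete gives 7.59, about 2 days too low. The whole bias comes from the 7.75% still shedding, with an implied average overrun of (9.57 − 7.59)/0.0775 = 25.5 days, so it depends on a long assumed tail. If the overrun averaged only 28 − 21 = 7 days, the bias would be 0.05 × 7 = 0.35 to 0.14 × 7 = 0.98 days. Episodes that ended before rescue are averaged correctly.

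**The case against.** The strongest reply is that the literal reading is not the intended one. SAP 2.5.3 expects trouble at some visits from Day 21, when most values are censored. If taking rescue at any time censored everything, Day 21 would not be a turning point. That suggests censoring by time, after rescue starts. This stands as a likely intention. But durations have no visit, and the sentence that governs them states neither an event order nor a censoring time.

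The reply also limits what may be inferred in four ways:

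- **That the mean duration changes method from visit to visit.** The documents do not support this. Durations are one value per participant; by-visit wording fits stool weight. The fallback is conditional on convergence problems and replaces only the mean, not the Lifetest median.
- **That zeros bias the mean upward.** The instruction "It will be set to 0 for participants with no clinical diarrhea illness" applies only to the number of days of clinical illness. Duration of illness is already restricted to those with the illness, and no Lifereg distribution is named from which a treatment of zeros could be deduced.
- **That censoring stool weight is meaningless.** If rescue lowers output, a post-rescue weight can be read as a lower bound on the rescue-free weight. The SAP does not state that assumption, but it is not incoherent.
- **That 86% applies to all infected participants.** It is an upper figure for participants with diarrhea and serves here only as an illustration.

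**Conclusion.** The point holds as a defect of specification. As worded, the duration rule censors nearly every infected participant's duration (27 of 27 at n = 30 and 90% infection) and leaves the median not estimable. An event-ordered rule would censor roughly 1 to 4 of 27, if the Protocol 4.1 shedding figures carry over and rescue falls on Day 21. The fallback biases the mean downward wherever unfinished values are averaged as complete. For time to end of shedding the bias is about 0.35 to 2 days under the assumptions shown; for stool weight the documents give no basis for a figure.

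A reader might infer that no duration at all can count as observed. That goes too far: it rests on the literal reading, and participants who take no rescue are not censored by this rule. A reader might also infer that the main results are at risk. They are not. The primary infection endpoint does not use this rule, and the Kaplan-Meier analyses of time to onset and time to resolution have event-ordered censoring. What is affected is a set of secondary descriptive summaries.

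**What to change.** In SAP 2.5.3:

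- Censor a number-of-days or duration value at the start of rescue only if the episode is still ongoing then. Otherwise count it as observed.
- Report the Kaplan-Meier median.
- Replace the Proc Means fallback with a not-estimable entry, or with a restricted mean over a stated horizon measured from episode onset. Day 21 counts from dosing and is not a common horizon for durations that start on different days.
- If Lifereg is kept, name its distribution and the variables it covers.
- Summarise stool weight before rescue as observed, and show post-rescue values separately.

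The permissive and mandatory wordings on who receives nitazoxanide should be reconciled, because the amount of censoring depends on them; no clinical rule is suggested here. Where rescue is given because diarrhea persists, the remaining censoring is informative, and the report should say so.

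The cost is SAP wording and modest reprogramming. The drawback is that the mean may be restricted, or not reported at some visits.
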